We used a wash-in, randomized, control study design consisting of four consecutive weeks of LT directed by physical therapists. For the first two weeks, participants received 6 bouts of LT. For the last 2 weeks, participants were randomized to receive 6 bouts of either 30 minutes of TSS coupled with LT or a sham-control stimulation coupled with LT. Primary outcome assessments for walking function and spasticity were conducted at the beginning and end of each 2-week intervention block (first 2-weeks [wash-in phase] and second 2-weeks [intervention phase]). The assessments at the end of each 2-week block were performed prior to the training on that day. Pre-post training assessments of spasticity and assessments of tolerability (see below) were performed on each training day.

Intervention

Intervention. LT approaches used in the study included treadmill-based training with or without body weight support and with or without manual or robotic assistance (Lokomat, Hocoma, Volketswil, Switzerland) as well as overground locomotor training with or without body weight support and with or without manual assistance. LT approaches for each participant were chosen by the treating therapist in accordance with standard clinical practice. LT duration was approximately 1 hour and included both setup and take down time of all equipment.

Transcutaneous Spinal Cord Stimulation (TSS). Electrical stimulation (50Hz, biphasic pulses) was applied using a portable electrotherapy device (Empi Continuum, DJO Global, Vista, CA, USA), as previously described (Estes, Iddings et al. 2017). Briefly, with the participant seated, the stimulating electrode (5 cm round electrode) was placed over vertebral levels T11/T12, identified via manual palpation and the reference electrode (10 cm x 15 cm butterfly electrode) was placed over the umbilicus. With the participant standing, the stimulator was turned on and

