LT+TSSsham groups in change in walking ability (speed, distance, step length asymmetry) and spasticity (pendulum test, clonus drop test, mSCI-SET) during the wash-in (LT only) period, and during the intervention (LT+TSS, LT+TSSsham) period. The Wilcoxon signed-ranks test was used to examine changes within each group during the 2 study periods. Significance was set at $\alpha = 0.05$ for all analyses. We did not adjust the significance level for multiple comparisons as our measures cannot be assumed to be independent (Hart and Bagiella 2012), and because such adjustments are known to increase the likelihood of false negatives (Type II errors) (KJ 1990, Perneger 1998, Nakagawa 2004, Hart and Bagiella 2012) which is problematic in preliminary studies. For within-group comparisons, we computed the effect sizes as these are considered more meaningful than p-values for clinical interpretation of results (Borenstein 1997, Nakagawa 2004, Lakens 2013). We computed the effect size using Hedges' *g*, as this approach is recommended for small samples (Lakens 2013). Effect sizes were interpreted per recommendations for rehabilitation studies as small effects, 0.08 to 0.15; medium effects, 0.19 to 0.36; and large effects, 0.41 to 0.67 (Kinney, Eakman et al. 2020).

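### Effect sizes are planned only within groups, so the randomised LT+TSS versus LT+TSSsham contrast gets a p-value but no estimate or interval; secondarily, non-independence does not justify unadjusted testing of the pendulum measure in two legs

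*Combined protocol and SAP*

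**What the plan says.** Unless stated otherwise, these points come from the Data analysis section.

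- **Design.** Study Design: after two weeks of LT alone, "participants were randomized to receive 6 bouts of either 30 minutes of TSS coupled with LT or a sham-control stimulation coupled with LT". Both arms therefore receive LT throughout. The Intervention section gives the sham the purpose of controlling for placebo effects.
- **Primary measures.** Outcome Measures names the 10MWT as primary for walking speed and the pendulum test, by first swing excursion (FSE), as primary for spasticity. Spasticity measures are analysed separately in the more and the less impaired leg, and neither leg is designated as primary.
- **Between groups.** Mann-Whitney tests compare change in LT+TSS and LT+TSSsham, once in the wash-in and once "during the intervention (LT+TSS, LT+TSSsham) period".
- **Within groups.** "The Wilcoxon signed-ranks test was used to examine changes within each group during the 2 study periods".
- **Effect sizes.** "For within-group comparisons, we computed the effect sizes as these are considered more meaningful than p-values for clinical interpretation of results". The statistic is Hedges' g, with benchmarks that run up to "large effects, 0.41 to 0.67". No effect size is described for the between-group comparison, and no confidence interval for any comparison.
- **Multiplicity.** The significance level is 0.05 for every analysis. The first reason for not adjusting is: "We did not adjust the significance level for multiple comparisons as our measures cannot be assumed to be independent". The second is that adjustment raises Type II error, "which is problematic in preliminary studies".

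**The concern.** The question of the trial is whether TSS adds to LT. Only the randomised contrast answers it, because LT, the passage of time and placebo response are present in both arms. The plan gives that contrast a p-value and keeps the quantity it finds more meaningful for changes within each arm. A reader who follows the plan's own preference will look at two within-arm values of g and two signed-rank results, and will have no estimate of what TSS added or of how uncertain it is.

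The multiplicity paragraph raises a second, smaller problem. Correlation between tests reduces the inflation from multiple testing but does not remove it, and it does not invalidate an adjustment. The matter is concrete for the primary spasticity measure, which has two chances at 0.05 because neither leg is named.

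**Working it through.** There is no figure of the plan to reproduce: 0.05 is a chosen threshold, and no sample size, power or overall error rate is given. Arm sizes, correlations between legs, the size of the LT effect and two-sided testing are assumptions below.

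**1. What each comparison contains** (treating effects as additive)

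- Intervention-period change, LT+TSS arm: LT + time + placebo + TSS.
- Intervention-period change, sham arm: LT + time + placebo.
- Difference between arms: TSS.
- Wash-in change, either arm: LT + time, with no stimulation and so no stimulation placebo.

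Setting the LT+TSS arm's intervention change against its own wash-in change leaves TSS + placebo + any difference in the LT and time effects between weeks 1-2 and weeks 3-4. The participants are 2 to 6 months after injury, so a constant time effect cannot be taken for granted.

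**2. Comparing within-arm significance when TSS does nothing**

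Let both arms improve by the same d (in SD of change) with normal changes, each tested by an exact two-sided signed-rank test at 0.05. If p is the chance that one arm shows significant improvement, then P(LT+TSS significant, sham not) = p(1 - p). At d = 0.5, p is about 0.19, 0.28 and 0.40 at 8, 10 and 14 per arm, giving 0.19 × 0.81 = 0.15, 0.28 × 0.72 = 0.20 and 0.40 × 0.60 = 0.24. Simulated values:

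| d | 8 per arm | 10 per arm | 14 per arm |
|---|---|---|---|
| 0.3 | 8.1% | 11.2% | 14.3% |
| 0.5 | 15.4% | 20.3% | 23.9% |
| 0.8 | 24.6% | 24.0% | 17.5% |

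The between-group Mann-Whitney test in the same simulations rejects in 4.3% to 5.0%.

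**3. Precision of the missing estimate**

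The 95% CI half-width for between-group g near zero is J × 1.96 × √(2/n), with J = 1 - 3/(4(2n - 2) - 1).

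- n = 8: 0.945 × 1.96 × 0.500 = 0.93
- n = 10: 0.958 × 1.96 × 0.447 = 0.84
- n = 14: 0.971 × 1.96 × 0.378 = 0.72

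All three exceed 0.67, the top of the plan's band for large effects.

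**4. Pendulum test in two legs, no true TSS effect**

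The bound under any dependence is 2 × 0.05 = 0.10. At independence, P(at least one leg significant) = 1 - 0.95² = 0.0975; in the direction of TSS benefit only, 1 - 0.975² = 0.0494. Other correlations come from the bivariate normal distribution. Under Holm, the smaller p-value must reach 0.025.

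| Correlation | Either direction | False TSS benefit | Either direction, Holm |
|---|---|---|---|
| 0 | 9.8% | 4.9% | 4.9% |
| 0.5 | 9.1% | 4.5% | 4.6% |
| 0.8 | 7.8% | 3.9% | 4.0% |
| 0.9 | 7.0% | 3.5% | 3.6% |

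The nominal rates for a single leg are 5% in either direction and 2.5% for benefit. Unadjusted error exceeds these at every correlation shown, and Holm stays below 5% at every one.

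The discreteness of exact tests is not a dependable safeguard. Exact Mann-Whitney size is 0.032, 0.050, 0.043 and 0.050 at 5, 8, 10 and 14 per arm. For two independent legs, 1 - (1 - size)² gives 6.2%, 9.7%, 8.5% and 9.7%.

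**The case against.** **The right test is already planned.** The between-group comparison comes first in the analysis text and names the intervention period. Nothing says that a TSS claim will be drawn by setting a significant arm against a non-significant one. This stands. The 15% to 24% describes a misreading that the plan leaves open, not one that it adopts. It does not supply the missing estimate.

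**The wash-in guards against crediting LT to TSS.** In part it does: each arm has its own LT-only reference change. It does not remove placebo or time effects from the intervention-period change, as step 1 shows.

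**Non-independence and Type II error may be one argument**, namely that adjusting correlated tests is over-conservative. The Holm column, falling from 4.9% to 3.6%, shows some conservatism. That supports the second reason; it does not make dependence a reason in itself. The Type II reason is defensible in a preliminary study.

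Three stronger readings are tempting and not supported:

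- A reader might infer that nearly 10% is the rate of false claims of TSS benefit. It counts both directions; the benefit rate is 3.5% to 4.9%.
- A reader might infer that a within-arm g in the large band, when TSS does nothing, is an error. With a true change of 0.5 SD, a g of 0.41 or more correctly classifies a real change, and the sham arm gets there equally often. The fault would lie in attributing it to TSS.
- A reader might infer that adjustment across all outcomes is obligatory or that the 10MWT result is inflated. The plan names two primary measures for two separate questions, and walking speed has one between-group test at 5% in the intervention period.

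**Conclusion.** The main point holds. The quantity that the plan prefers for interpretation is not planned for the one comparison that isolates TSS, and no confidence interval is described for it. If within-arm results were compared in place of the planned Mann-Whitney test, a spurious contrast would appear in about 15%, 20% and 24% of trials at 8, 10 and 14 per arm with an equal 0.5 SD improvement. The range over 0.3 to 0.8 SD is 8% to 25%. All of these inputs are assumed.

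The secondary point also holds, with a modest size. Non-independence is not a valid reason to omit adjustment. For the primary pendulum measure, the chance of a false significant result in at least one leg is 7.0% to 9.8%, at most 10%, and of a false TSS benefit 3.5% to 4.9% against 2.5%. This assumes two-sided tests that attain 0.05 and correlations between 0 and 0.9.

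The documents do not support the inference that the decision not to adjust is itself wrong, or that TSS claims will rest on within-group changes. The lack of an express exploratory label is mostly a matter of wording, since the text already places the study among preliminary ones.

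**What to change.** 1. For intervention-period change in 10MWT speed and pendulum FSE (each leg), report the LT+TSS versus LT+TSSsham estimate with a 95% CI: the Hodges-Lehmann shift, which matches the Mann-Whitney test, a between-group Hedges' g, or both. State that any TSS claim rests on this contrast and that within-group changes are descriptive.
2. Delete the non-independence reason and keep the Type II reason.
3. For the pendulum test, apply Holm over the two legs, or report both legs and claim no 5% error for the measure as a whole. Holm needs no choice of leg. That is an advantage here: the text is in the past tense, so a leg named now may be post hoc.

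The estimates use data already collected; the rest is wording. The intervals will be wide (step 3), which is what a reader of a small study needs to see. Holm costs some power: at its first step of 0.025, a test with an assumed 80% power at 0.05 has Φ(1.960 + 0.842 - 2.241) = 71%. With only 4 per arm, an exact Mann-Whitney test could not pass that step, because its smallest two-sided p-value is 2/70 = 0.029; with 5 per arm it is 2/252 = 0.008. Adjustment across the walking and spasticity primaries is optional. With each held at 5%, the chance of at least one false primary result is at most 10%.

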adjusted to a level at which the participant reported sensations of tingling in the legs and feet or to the highest level the participant could tolerate. participants were standing. For those with impaired sensation as well as those with sensation, target stimulation was subthreshold for lower extremity muscle activation and verified by the absence of visible muscle contraction. Stimulation was delivered for 30 minutes at the target stimulation intensity and occurred concomitantly with LT. Following 30 minutes of stimulation, the intensity was ramped down and the stimulation unit was turned off and disconnected. If LT finished prior to the 30 minutes of stimulation, then participants completed their 30 minutes of stimulation while seated on a high-lo mat where training day assessments would occur. Conversely, if the 30 minutes of stimulation finished prior to the end of LT, then the LT session was completed prior to the assessments.

Sham-control stimulation -- TSSsham. The sham-control was designed to control for placebo effects associated with the perception of intervention. For the TSSsham, a 2-inch round electrode was placed over T11/T12 and a reference electrode was placed over the umbilicus, as performed with TSS. The intensity of electrical stimulation was briefly ramped up to a level at which the participants reported perceiving the stimulation, then ramped down and turned off for the remainder of the intervention. The stimulator and electrodes remained attached to the participant for 30 minutes of the LT session, similar to the active TSS intervention. After 30 minutes, the stimulator unit was disconnected from the electrode leads.

Outcome Measures

Walking Assessments:

All walking-related data were captured during overground walking; participants were given the standardized instruction “walk as quickly and safely as possible”. Participants wore a gait belt during walking assessments and were guarded by a physical therapist for safety. During testing, participants used the walking assistive and orthotic devices they typically used during therapy, however no body weight support was provided during testing.

10-Meter Walk Test (10MWT). We utilized the 10MWT, which was our primary outcome measure for walking speed to assess changes in walking speed at the beginning and end of each 2-week LT block. A stopwatch was used to capture walking speed. Participants completed 3 walks in each assessment session with a 2 min rest between trials.

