Spinal Cord Assessment Tool for Spastic Reflexes (SCATS). The SCATS was used as a clinical measure of spasticity that has been shown to be reliable and valid in persons with SCI (Benz, Hornby et al. 2005). The SCATS was performed on each leg immediately before and after every intervention session by masked clinical assessors. Assessors rated clonus, flexor spasms, and extensor spasms, on a 4-point scale for each lower extremity. For clonus and extensor spasms the scale was as follows: 0-no reaction, 1-mild lasting <3 seconds, 2- moderate lasting 3-10 seconds, and 3- severe lasting >10 seconds. The scale for flexor spasms was determined by measuring degrees of flexion at the knee and hip on the following scale: 0- no reaction, 1- mild <10 degrees, 2- moderate 10-30 degrees, 3- severe >30 degrees.

Tolerability of stimulation. During the 2-week intervention period, participants were asked to rate the tolerability of their stimulation (LT+TSS and LT+TSSsham). Using a numeric rating scale (NRS) from 0 to 10, participants were asked how tolerable the stimulation was in regard to pain, with 0 being no pain and 10 being the worst pain imaginable. Responses were taken prior to the start of the stimulation to determine baseline tolerability, and then 1 minute and 30 minutes during stimulation.

Data analysis

Data were analyzed using SPSS (version 26; SPSS Inc., Chicago, IL, USA). Numerical and ordinal data were presented as the mean(SD) and median(IQR), respectively. For spasticity measures, data in the more- and less-impaired legs (as determined by lower extremity motor score [LEMS]), were analyzed separately. Due to our small sample size, nonparametric tests were performed (Portney and Watkins 2009). Mann-Whitney U tests were conducted to examine differences between the LT+TSS and

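### Effect sizes are planned only for change within each arm; the randomised comparison of LT+TSS with LT+TSSsham gets a p-value but no estimate and no interval

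*Combined protocol and SAP*

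**What the plan says.** Under Study Design, everyone first has LT alone ("For the first two weeks, participants received 6 bouts of LT"). For the last two weeks "participants were randomized to receive 6 bouts of either 30 minutes of TSS coupled with LT or a sham-control stimulation coupled with LT". The Sham-control stimulation paragraph gives the reason for the second arm: "The sham-control was designed to control for placebo effects associated with the perception of intervention".

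The Data analysis section then sets out three things:

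- **Between arms.** "Mann-Whitney U tests were conducted to examine differences between the LT+TSS and" sham groups in change in the walking and spasticity measures, for the wash-in and for the intervention period. No effect measure or interval accompanies this test.
- **Within arms.** "The Wilcoxon signed-ranks test was used to examine changes within each group during the 2 study periods".
- **Effect sizes.** "For within-group comparisons, we computed the effect sizes as these are considered more meaningful than p-values for clinical interpretation of results". The measure is Hedges' g, read against bands that end with "large effects, 0.41 to 0.67". Nothing extends g to the between-arm comparison, and the SD that standardises it is not named.

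The only other summaries are descriptive: "Numerical and ordinal data were presented as the mean(SD) and median(IQR), respectively". No confidence interval is described for any comparison.

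**The concern.** The plan argues that effect sizes tell the clinician more than p-values. It then gives the randomised contrast only a p-value and attaches the effect size to a comparison that was not randomised.

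Change within the LT+TSS arm combines any stimulation effect with two weeks of LT, recovery at 2–6 months post injury (Subjects), retest, and the placebo response that the sham was included to remove. Within-arm g makes no use of the sham arm. The LT-only wash-in gives each arm a partial reference, but no test between periods is described, and recovery need not be linear.

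The text appeals to the needs of preliminary studies. The most useful thing such a study can hand on is the size of the stimulation effect and its uncertainty, and the plan does not call for either. Readers steered towards effect sizes would get labelled values that answer a different question.

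**Working it through.** There is no figure in the plan to reproduce: the documents state no sample size, SD, expected change or target effect. The textual point rests on the passages above. The arithmetic below shows what could follow.

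**Assumptions, none from the documents:** 8 per arm (12 as a check); normal change scores; no stimulation effect, so both arms truly change by the same *d* SDs of change; two-sided exact tests at 0.05. From the plan: alpha 0.05, and 0.41 as the lower edge of the large band.

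**1. Chance that within-arm g reaches 0.41 in the improving direction.** Standardise by the SD of change, with small-sample factor J = 1 - 3/(4·df - 1). For n = 8, df = 7 and J = 1 - 3/27 = 0.889. Then g ≥ 0.41 means mean/SD ≥ 0.41/0.889 = 0.461, or t ≥ 0.461 × √8 = 1.305. The chance is the upper tail of a noncentral t with 7 df and noncentrality d√8; call it p.

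**2. Chance that LT+TSS reaches 0.41 and sham does not.** The arms are independent, so this is p(1 - p).

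**3. Chance that LT+TSS alone is Wilcoxon-significant.** If w is the chance that one arm is significant (simulated, 100,000 replicates), this is about w(1 - w); the table shows the simulated rate.

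| True change in both arms (SD) | LT+TSS g ≥ 0.41 | LT+TSS g ≥ 0.41, sham below | One arm Wilcoxon-significant | LT+TSS alone significant |
|---|---|---|---|---|
| 0 | 12% | 10% | 4% | 4% |
| 0.3 | 35% | 23% | 9% | 8% |
| 0.6 | 66% | 22% | 26% | 19% |
| 0.8 | 83% | 14% | 43% | 24% |
| 1.0 | 93% | 6% | 61% | 24% |

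Mann-Whitney stays at 5% throughout. At 12 per arm, LT+TSS alone is significant in 4%, 12%, 24%, 22% and 13%.

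The standardiser matters. If g uses the pre/post SD with correlation 0.7, the first column becomes 6%, 23%, 52%, 72% and 87%.

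**4. Reading the LT+TSS arm against its own wash-in.** With equal true change in both periods, significance in the intervention period but not in the wash-in occurs in 4%, 8%, 20%, 25% and 24%. The wash-in does not remove the risk.

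**5. What a between-arm g would show.** For n = 8, df = 14 and J = 1 - 3/55 = 0.945. Then g ≥ 0.41 needs t ≥ (0.41/0.945) × √(8/2) = 0.867, which has chance 20% with no stimulation effect, whatever the shared change. At 12 per arm it is 15%. The point estimate therefore needs its interval. With SE = √(2/n + g²/(4n)):

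- n = 8: √(0.25 + 0.1681/32) = 0.505; 95% CI 0.41 ± 1.96 × 0.505 = -0.58 to 1.40.
- n = 12: √(0.1667 + 0.1681/48) = 0.413; 95% CI -0.40 to 1.22.

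Applying the small-sample factor to the SE as well narrows the first to -0.53 to 1.35, with the same message.

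**The case against.** The strongest reply is that the randomised contrast is tested, in both periods, by a valid method. The plan never says that within-arm g measures the stimulation effect, and it states no rule that infers efficacy when LT+TSS is significant and sham is not. All of that is right. It limits the point to a misplaced effect size and a risk of misreading.

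Some of the numbers also need care:

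- A g above 0.41 in 93% of trials when an arm truly changes by 1.0 SD is a correct label for a large change, not a false signal. Sham g would presumably be shown beside it, so the fairer measure of misreading is the LT+TSS-large, sham-not rate: 6–25% across shared changes of 0 to 1.0 SD, peaking near 0.5 SD.
- The Wilcoxon rates apply only if arms are read side by side. They are not the plan's error rate, and the 4% at no change counts both directions (about 1.9% in the improving direction).
- Moving g to the between-arm contrast does not by itself cut chance findings much. A gap of at least 0.41 between the two within-arm values occurs in 20–25% of trials, against 20% for a between-arm g of that size. Most of the protection comes from the interval.

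A reader could also derive the contrast from means and SDs, but only if change scores are reported by arm, which the plan does not promise. None of this supplies the missing estimate or its uncertainty.

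**Conclusion.** The concern holds and should be fixed. As written, the plan yields labelled effect sizes that do not isolate stimulation, and only a p-value for the comparison that does. This is not an invalid test and not an inflated error rate in the plan's own procedure.

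If the two arms' labels are compared, a favourable but spurious contrast could appear in roughly one trial in four at moderate shared improvement (23% at 0.3 SD, 22% at 0.6 SD). A proper between-arm interval would instead show that effects in both directions remain plausible.

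The textual finding needs no assumption. Every rate and interval rests on assumed arm sizes of 8 or 12, normal change scores, a shared true change and, for within-arm g, a chosen standardiser.

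**What to change.** Add two or three sentences to the Data analysis section:

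- For each outcome's intervention-phase change, report beside the Mann-Whitney p-value the between-arm Hodges-Lehmann shift in the outcome's own units (for example m/s, metres or degrees) and the independent-groups Hedges' g with pooled SD, each with a 95% CI. If only one is kept, one between-arm estimate with its CI is the minimum.
- Base statements about the effect of stimulation on that contrast, and give a small, medium or large label only together with its CI.
- Keep the within-arm Wilcoxon tests and within-arm g, for both periods, as descriptive, and state which SD standardises the within-arm g.

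The cost is a few lines of analysis on data already collected. The downside is that at about 8 per arm the intervals will span every label in both directions, so the labels will say less and look less favourable.

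### Within-group effect sizes are ranked above p-values, yet they are labelled from bands with gaps and no open top and reported without confidence intervals, so a label can present chance change as a meaningful effect

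*Combined protocol and SAP*

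**What the plan says.** All of this is in the Data analysis section of the combined protocol and SAP.

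- **Tests.** Between-group differences in change are tested with Mann-Whitney U. Within groups, "The Wilcoxon signed-ranks test was used to examine changes within each group during the 2 study periods". The stated reason for rank tests is sample size: "Due to our small sample size, nonparametric tests were performed". No number of participants is given.
- **Role of the effect size.** "For within-group comparisons, we computed the effect sizes as these are considered more meaningful than p-values for clinical interpretation of results".
- **Estimator.** Hedges' g is named as suited to small samples. The text does not say which SD divides the mean change (SD of change, baseline SD, or an average of the two raw SDs), and it mentions no confidence interval.
- **Labels.** "small effects, 0.08 to 0.15; medium effects, 0.19 to 0.36; and large effects, 0.41 to 0.67".
- **Number of comparisons.** Spasticity measures are analysed separately for "data in the more- and less-impaired legs", and no multiplicity adjustment is made.

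**The concern.** A verbal label attached to a point estimate carries the clinical reading of within-group change, and the plan prefers that reading to the p-value. Three features make the label fragile.

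1. The bands do not meet, so some ordinary values of g have no label. The top band also stops at 0.67 without saying what lies above it.
2. The bands are only 0.07, 0.17 and 0.26 wide. With few participants, the sampling error of g can be larger than that. Without an interval, the reader cannot tell whether a label reflects a change or noise.
3. For paired data, the size of g depends on the standardiser, which is left open.

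If this stands, a report could describe several within-group changes as medium or large when the data are compatible with no change. The missing interval is the main problem.

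**Working it through.** **Inputs from the documents.** The three bands and the within-group scope come from the Data analysis section. There are 8 measures: speed, distance, step length asymmetry, pendulum test in two legs, drop test in two legs, and mSCI-SET. With 2 groups and 2 periods this gives 8 × 2 × 2 = 32 within-group values, if g is computed for each.

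**Assumptions (not in the documents).** n = 8 per arm, with 5 and 20 as a range; pre-post correlation r = 0.8 to 0.95; normal data with equal pre and post SDs. The plan states no figure of its own to reproduce.

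**Step 1. Gaps.** At two decimals, 0.16-0.18 and 0.37-0.40 have no label, and neither has anything below 0.08 or above 0.67. With no true change and the SD of change as divisor, about 10-11% of estimates fall in the two inner gaps for n = 5 to 20. With the average raw SD the share can be lower: at n = 20 it is 5.5% at r = 0.9 and 2.1% at r = 0.95.

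**Step 2. Chance of reaching 0.41 with no true change, SD of change.** Here g = J × t/√n, with J = 1 − 3/(4(n−1) − 1).

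- n = 8: J = 1 − 3/27 = 0.889. |g| ≥ 0.41 means |t| ≥ 0.41 × √8/0.889 = 1.305 on 7 df, two-sided probability 0.233. Expected count: 0.233 × 32 = 7.5, about 7 of 32.
- n = 5: J = 0.80, |t| ≥ 1.146 on 4 df, probability 0.32.
- n = 20: J = 0.96, |t| ≥ 1.910 on 19 df, probability 0.07.

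Expected counts hold even when the measures are correlated; the actual count then varies more.

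**Step 3. The same chance with the average of the pre and post SDs.** Simulated at n = 8:

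| r | P(abs. g ≥ 0.41) | Expected of 32 |
|---|---|---|
| 0.8 | 7% | about 2 |
| 0.9 | 2% | about 0.6 |
| 0.95 | 0.4% | about 0.1 |

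The rate therefore runs from 23% to 0.4% at one sample size, depending on a choice the plan leaves open and a correlation it does not give.

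**Step 4. Interval around one estimate.** At n = 8, take an observed mean change of 0.40 SDs of change, before the small-sample correction (corrected g = 0.889 × 0.40 = 0.36, labelled medium). t = 0.40 × √8 = 1.13. Inverting the noncentral t on 7 df gives a 95% CI of −0.34 to 1.11. This contains zero and all three bands.

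**Step 5. Standardiser.** g(SD of change) = g(average raw SD)/√(2(1−r)). The ratio is 1.58, 2.24 and 3.16 at r = 0.8, 0.9 and 0.95. A change of 0.30 raw SD, labelled medium, becomes 0.47 (large), 0.67 (top of large) and 0.95 (beyond the printed bands).

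**The case against.** The strongest reply is that this is a secondary, within-group description in a study the plan calls preliminary. The randomised comparison is the Mann-Whitney test, which uses neither g nor the bands. That stands, and it limits the point to interpretation. Nothing in the text makes g a success criterion.

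Four stronger readings are tempting, and the documents do not support them.

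- *The largest effects go unclassified.* Literally, nothing above 0.67 has a label, but a reader will take 0.9 as large and 0.03 as negligible. The real ambiguity is in the two inner gaps; the open top only needs stating.
- *Every interval spans every band.* At n = 8 with the SD of change, an observed 1.5 has a 95% CI of 0.44 to 2.51, which excludes the small and medium bands.
- *The same data can read small or large.* That needs a ratio of at least 0.41/0.15 = 2.73, so r of about 0.93 or more. No r is given. A shift from medium to large needs much less.
- *About 7 of 32 values would read large by chance.* This holds only for the SD of change at n = 8. With the average raw SD and high r it is 2 or fewer.

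The cited sources may close the gaps or name a standardiser. That cannot be checked here; the plan's own text does neither.

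**Conclusion.** The point holds as a weakness in how within-group results are interpreted, and it should be corrected. The gaps, the closed top and the absence of an interval can be read directly from the text. The unnamed standardiser is, by itself, only missing detail; it matters because it changes both the label and the chance rate.

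The size depends on figures the documents do not give. With no true change, the share of estimates at or above 0.41 is 32%, 23% and 7% for n = 5, 8 and 20 with the SD of change, but 7% down to 0.4% at n = 8 with the average raw SD and r from 0.8 to 0.95. The claim is therefore that a label on the point estimate alone *can* present chance change as meaningful. It does not follow that labels are generally noise: a large true change would still tend to give a large g. A reader might also infer that the trial's between-group conclusions are affected; they are not.

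**What to change.** 1. Report every within-group g with its 95% CI, and interpret the label together with that interval.
2. Make the bands contiguous, with large open-ended at the top. The rule for closing the gaps is for the sponsor to choose and state.
3. State one standardiser for all measures, for example the average of the pre and post SDs, so that the size of g does not depend on the pre-post correlation.

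Labels need not be withheld when the interval includes zero. That would bring back a significance filter, against the plan's own reason for using effect sizes.

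The cost is a few sentences in the analysis plan and one extra column in the results tables; no new data are needed. The downside is that favourable labels will look less certain.
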